- Not discontinued patients: the first administration date of Humira + 392 days

Even if there is one adverse reaction, it should be counted as one patient in every period when the reaction persisted.

"2.7 Incidence of adverse reactions per set period"

Patients for analysis: patients in the safety analysis group

Analysis objective: to show the onset status of adverse reactions per onset period.

Analysis item: aggregate the following items by period for adverse reactions which occurred in the safety analysis period.

Calculate the number of patients and the percentage to the number of patients surveyed per number of patients surveyed, number of patients with adverse reactions, etc. type of adverse reactions, etc. (SOC, PT).

Note: Refer to the note of "2.6 Incidence of adverse reactions per onset period (serious)".

"2.9 Incidence of adverse reactions (serious adverse reactions/adverse reactions) per background factor"

Patients for analysis: patients in the safety analysis group

Analysis objective: to show the incidence of adverse reactions per patient background factor and

analyze them.

Analysis items: calculate the number of all patients, the percentage to the number of patients with serious adverse reactions and all patients, the number of patients with adverse reactions and the percentage to number of all patients, the tests for adverse reactions (Fisher's exact test for nominal-scale factors and Man-Whitney's u test for ordinal-scale factors) per the following patient background factor regarding the adverse reactions which occurred in the safety analysis period.

Note: the patient background factors are as follows:

Age (year), the elderly, pediatrics, sex, body weight (kg), BMI (kg/m²), duration of illness (year), complications, complication: hepatic function disorder, complication; renal impairment, complication: blood disorder, complication: respiratory disorder, complication: diabetes mellitus, complication: osteoporosis, complication: malignant tumour, medical history, medical history: tuberculosis, medical history: non-tuberculous mycobacteriosis, medical history: interstitial pneumonia, medical history: bronchitis bacterial, medical history: aplastic anaemia, medical history: pancytopenia, medical history: malignant tumour, allergy history, smoking history, detailed history of smoking history, the administration status of Humira: self-administration, prior medication, prior medication: biological product, prior medication Infliximab, prior medication: other biological product, prior medication: aminosalicylic acid drug, prior medication: corticosteroids, prior medication: azathioprine, prior medication 6-mercaptopurine, prior medication: azathioprine & 6-mercaptopurine, prior medication: tacrolimus & ciclosporin, prior treatment, prior treatment: leukocytapheresis, prior treatment: surgery, prior treatment: enteral nutrition therapy, prior treatment: intravenous nutrition therapy, concomitant medication, concomitant medication: aminosalicylic acid drug, concomitant medication: corticosteroids, concomitant medication: azathioprine, concomitant medication: 6-mercaptopurine, concomitant medication: azathioprine & 6-mercaptopurine, concomitant medication: tacrolimus & ciclosporin, concomitant treatment, concomitant treatment: leukocytapheresis, concomitant treatment: surgery, concomitant treatment: intravenous nutrition therapy, concomitant treatment: enteral nutrition therapy, site of disease by type, partial Mayo score, CRP

"2.9.xx Incidence of adverse reactions per background factor and seriousness"

Patients for analysis: patients in the safety analysis group

Analysis objective: to show the onset status of non-serious/serious adverse reactions per statistically-significant background factor based on the test results in 2.9.

Analysis item: aggregate the following items per background factor and seriousness for adverse reactions which occurred in the safety analysis period.

Calculate the number of patients and the percentage to the number of patients surveyed per number of patients surveyed, number of patients with adverse reactions, incidence of the reactions, number of adverse reactions and type of adverse reactions (SOC, PT).

"2.13.1 Incidence of adverse reactions with/without hepatic function disorder and per seriousness"

Patients for analysis: patients in the safety analysis group

Analysis objective: to show the onset status of non-serious/serious adverse reactions with/without hepatic function disorder

Analysis item: aggregate the following items with/without hepatic function disorder per seriousness regarding the adverse reactions which occurred in the safety analysis period.

Calculate the number of patients and the percentage to the number of patients surveyed per number of patients surveyed, number of patients with adverse reactions, incidence of the reactions, number of adverse reactions and type of adverse reactions (SOC, PT).

Note: Aggregate the most serious reaction among the identical PTs in a patient.

When calculating the number of patients with the target events, remove unnecessary data per case number and seriousness. When calculating the number of SOC, remove unnecessary data per case number, seriousness and SOC.

"2.14.1 Incidence of adverse reactions with/without renal impairment and per seriousness" Patients for analysis: patients in the safety analysis group

Analysis objective: to show the onset status of non-serious/serious adverse reactions with/without renal impairment

Analysis items: aggregate the following items with/without renal impairment per seriousness regarding the adverse reactions which occurred in the safety analysis period.

Calculate the number of patients and the percentage to the number of patients surveyed per number of patients surveyed, number of patients with adverse reactions, incidence of the reactions, number of adverse reactions and type of adverse reactions (SOC, PT).

Note: refer to the note of "2.13.1 Incidence of adverse reactions with/without hepatic function disorder and per seriousness".

"2.15.1 Incidence of adverse reactions per seriousness in pediatrics and non-pediatrics"

Patients for analysis: patients in the safety analysis group

Analysis objective: to show the onset status of adverse reactions in pediatrics and non-pediatrics per outcome.

Analysis items: aggregate the following items per seriousness in pediatrics and non-pediatrics regarding adverse reactions which occurred in the safety analysis period.

Calculate the number of patients and the percentage to the number of patients surveyed per number of patients surveyed, number of patients with adverse reactions, incidence of the reactions, number

of adverse reactions and type of adverse reactions (SOC, PT).

Note: refer to the note of "2.13.1 Incidence of adverse reactions with/without hepatic function disorder and per seriousness".

"2.16.1 Incidence of adverse reactions per seriousness in the elderly and non-elderly patients" Patients for analysis: patients in the safety analysis group

Analysis objective: to show the onset status of non-serious/serious adverse reactions in the elderly and non-elderly patients.

Analysis items: aggregate the following items per seriousness in the elderly and non-elderly patients regarding adverse reactions which occurred in the safety analysis period.

Calculate the number of patients and the percentage to the number of patients surveyed per number of patients surveyed, number of patients with adverse reactions, incidence of the reactions, number of adverse reactions and type of adverse reactions (SOC, PT).

Note: refer to the note of "2.13.1 Incidence of adverse reactions with/without hepatic function disorder and per seriousness".

"2.17 A list of the onset status of adverse reactions/infections in this survey"

Patients for analysis: patients in the safety analysis group

Analysis objective: to show the onset status of adverse reactions, etc. and serious adverse reactions, etc.

Analysis item: aggregate adverse reactions and serious adverse reactions regarding the following items based on the adverse reactions which occurred in the safety analysis period.

Calculate the number of patients and the percentage to the number of patients surveyed per number of patients surveyed, number of patients with adverse reactions, etc. number of adverse reactions, incidence of adverse reactions, etc., and type of adverse reactions, etc. (SOC, PT).

Note: refer to the note of "2.13.1 Incidence of adverse reactions with/without hepatic function disorder and per seriousness" for serious adverse reactions.

"2.18 A list of the onset status of adverse reactions with/without treatment history with biological products".

Patients for analysis: patients in the safety analysis group

Analysis objective: to show the onset status of adverse reactions with/without treatment history with biological products.

Analysis item: aggregate the following items with/without treatment history with biological products for adverse reactions which occurred in the safety analysis period.

Calculate the number of patients and the percentage to the number of patients surveyed per number of patients surveyed, number of patients with adverse reactions, incidence of the reactions, number of adverse reactions and type of adverse reactions (SOC, PT).

"2.18.1 A list of the onset status with/without treatment history with biological products (patients excluded from the safety analysis group)"

Patients for analysis: patients excluded from the safety analysis group

Analysis objective: to show the onset status of adverse reactions with/without treatment history with biological products.

Analysis item: aggregate the following items with/without treatment history with biological products for adverse reactions which occurred in the safety analysis period.

Calculate the number of patients and the percentage to the number of patients surveyed per number of patients surveyed, number of patients with adverse reactions, incidence of the reactions, number of adverse reactions and type of adverse reactions (SOC, PT).

"2.19 A list of the onset status of adverse events in this survey"

Patients for analysis: patients in the safety analysis group

Analysis objective: to show the onset status of adverse events, serious adverse events and non-serious adverse events.

Analysis items: aggregate adverse events, serious adverse events and non-serious adverse events regarding the following items among adverse events which occurred in the safety analysis period.

Calculate the number of patients and the percentage to the number of patients surveyed per number of patients surveyed, number of patients with adverse reactions, number of adverse reactions, incidence of the reactions, type of adverse events (SOC, PT).

Note: When more than one identical PT is found in a patient, aggregate the event as 1 patient (case) in the following manner:

• Seriousness priority: serious > non-serious

"2.20 A list of the onset status of adverse reactions (all cases)"

Patients for analysis: patients in the safety analysis group

Analysis objective: to calculate the following items by seriousness for adverse reactions which occurred in the safety analysis period. Calculate the number of patients and the percentage to the number of patients surveyed per number of patients with adverse reactions, incidence of the reactions, number of adverse reactions and type of adverse reactions (SOC, PT). In addition, show the number of cases per days to outcome (recovered or recovering), number of patients per outcome, summary statistics of days to the onset per type of adverse reactions (PT).

Note: When more than one identical PT is found in a patient, aggregate seriousness, days to the onset, outcome and days to the outcome (recovered or recovering) as 1 patient (case) in the following manner.

• Seriousness priority: serious > non-serious

• Days to the onset: identify the days as mentioned in "days from the first administration date of Humira to the adverse-event onset date" defined in "10.2 Safety analysis".

• Outcome: identify it as mentioned in "outcome" defined in "10.2 Safety analysis".

 Days to outcome (recovered or recovering): identify the days as mentioned in "days from the first administration date of Humira to the outcome confirmation date (recovered or recovering)" defined in "10.2 Safety analysis".

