HUMIRA® for Subcutaneous Injection Protocol for Special investigation on Long-Term administration Ulcerative Colitis

AbbVie GK

1. Purpose of Surveillance

The following were investigated in the Special investigation on Long-Term administration of "HUMIRA® for Subcutaneous Injection (Nonproprietary name: Adalimumab (Genetical Recombination)" in patients with ulcerative colitis.

- 1. Unknown adverse drug reactions (ADRs) (especially important ADRs)
- 2. Incidence and conditions of occurrence of adverse reactions in the clinical setting
- 3. Factors that may affect the safety and efficacy of Humira
- < Priority items of investigation >

Infection, tuberculosis, malignant tumor, injection site reaction, autoimmune disease, pancytopenia, demyelinating disorders, congestive cardiac failure, and interstitial pneumonia For enteral infection, the cause (virus or bacteria) will be examined.

2. Sample Size

The number of patients to be included: 1500

They are patients with ulcerative colitis who use this drug after approval.

- < Rationale for setting >
- 1. Since this survey will be conducted in actual clinical practice, the proportion of patients who have been treated with anti-TNF α products is anticipated to be high. First, considering that a dropout rate may be higher than that in Japanese clinical studies due to the enrollment of such patients, the planned sample size was calculated by assuming a dropout rate at Week 52 of 70%. Next, in the all-case survey in patients with Crohn's disease, the CDAI, an efficacy endpoint, was not recorded for approximately 30% of all the patients. Thus, by assuming the proportion of patients without assessment of Mayo score of 30%, a remission rate of 30% and the accuracy of 95% confidence interval estimation of \pm 5%, the sample size was determined to be 1500 patients (Table 1).

Table 1 Sample size calculated based on the dropout rate and accuracy

Dropout rate 70%					
Sample size	Sample size at Week 52	No. of patients assessed for Mayo score	Remission rate 30% at Week 52 95%CI	Accuracy	
500	150	105	21.2~38.8	±8.8%	
1000	300	210	23.8~36.2	±6.2%	
1500	450	315	24.9~35.1	±5.1%	
2000	600	420	25.6~34.4	±4.4%	

No. of patients assessed for Mayo score is calculated 70% of sample size at Week 52.

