4.1. Survey objective

This survey aims at exploring the following items in colitis ulcerative patients who used Humira, as the special drug-use survey of Humira [®] for subcutaneous use only (the long-term survey).

- 1) Unexpected adverse reactions (Specifically important adverse reactions)
- 2) The onset status of adverse reactions in the practical use
- 3) Factors which may affect the safety and effectiveness

<Priority survey items>

The onset status of infection, tuberculosis, malignant tumour, administration site reactions, autoimmune disease, pancytopenia, demyelinating disease, cardiac failure congestive and interstitial pneumonia

If an intestinal infection occurs, investigate the virus or bacterium causing it whenever possible.

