9.5. Statistical test method

The test does not include the classification of unknown/not provided. In principle, the first layer is subjected to the intersegmental test of classified data. When adjusting multiplicity, describe it in each chart of Chapter 13.

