9.6. Significant level

In principle, the significant level is 5%, two-tailed. p<0.05 (<5%) shall be considered significant.

10. Derivation and calculation methods for data

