13.3. Effectiveness

"3.1.1 Changes in Mayo score (Observed Case)"

Patients for analysis: patients in the effectiveness analysis group

Analysis objective: to show Mayo score and the changes in Mayo score per assessment period.

Analysis item: calculate the number of patients in the analysis groups.

Calculate the number of target patients, the mean and standard deviation of Mayo score, the mean and standard deviation of changes in Mayo score for each assessment period, and conduct a paired-t test which compares the values at the initial administration.

Note: Follow "12.3 Assessment period for Mayo score" for Time Allowance of assessment period.

The analysis covers only the patients with the assessment applicable to Time Allowance of the first administration and each assessment period.

Multiplicity in the test will be adjusted by the Bonferroni method.

"3.1.2 Changes in the remission rate at each point of Mayo score (Observed Case)"

Patients for analysis: patients in the effectiveness analysis group

Analysis objective: to show the remission rate of Mayo score per assessment period.

Analysis item: calculate the number of patients in the analysis groups.

Calculate the number of target patients, the percentage to the number of patients who achieved a remission and the number of target patients, 95%CI of the remission rate, and conduct a McNemar test for the first administration per assessment period.

In addition, prepare a line plot to describe the percentage to the target patients among the patients who achieved a remission per assessment period.

X-axis: assessment period (in week)

Y-axis: percentage (%)

Note: Follow "12.3 Assessment period for Mayo score" for Time Allowance of assessment period.

The analysis covers only the patients with the assessment applicable to Time Allowance of the first administration and each assessment period.

For the confidence interval, use the Clopper-Pearson's confidence interval.

Refer to "10.3 Effectiveness analysis" for the calculation method and remission rate.

"3.1.4 Changes in partial Mayo score (Observed Case)"

Patients for analysis: patients in the effectiveness analysis group

Analysis objective: to show partial Mayo score and the changes in partial Mayo score per assessment period.

Analysis item: calculate the number of patients in the analysis groups.

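### Objective 3 rests on 57 single-factor tests per table at an unadjusted 5%, with no comparative estimate, confidence interval or adjustment for other factors, so a significant factor may be confounded or due to chance

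*SAP*

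**What the plan says.** Protocol section 1 lists as its third purpose "Factors that may affect the safety and efficacy of Humira", and SAP 4.1 repeats it as "Factors which may affect the safety and effectiveness".

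Three tables test factors against an outcome: 2.9 (adverse reactions), 3.4 (general improvement) and 3.4.1 (remission on the partial Mayo score at final assessment). Table 2.9 applies Fisher's "exact test for nominal-scale factors and" the Mann-Whitney test for ordinal factors, one test per factor. Tables 3.4 and 3.4.1 do the same with the same factor list. All three give numbers and percentages by factor level.

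On error control, SAP 9.6 says "In principle, the significant level is 5%, two-tailed" and that "p<0.05 (<5%) shall be considered significant". SAP 9.5 adds: "When adjusting multiplicity, describe it in each chart of Chapter 13". Tables 3.1.1 and 3.1.4 carry such a line ("Multiplicity in the test will be adjusted by the Bonferroni method"). Tables 2.9, 3.4 and 3.4.1 do not, so by the SAP's own rule they are unadjusted.

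Table 2.9.xx then gives a breakdown by seriousness for each "statistically-significant background factor based on the test results in 2.9". Neither document names a regression or any other covariate-adjusted analysis.

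**The concern.** Patients were not randomised to any of these factors, and many are plausibly linked: earlier biologic use, steroid and thiopurine use, baseline partial Mayo score and CRP may all reflect how severe or refractory the disease is. The plan itself assumes a large effect of one of them, with Week 52 remission of 10% in patients with anti-TNF history and 30% in those without (Protocol section 2, Table 2). Any factor associated with that history could look significant without an effect of its own, and a single-factor p-value cannot tell the two cases apart.

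Some listed factors are also not fixed at baseline. SAP 10.1 counts a drug as concomitant if its use overlaps Humira treatment at any point, and self-administration needs one tick at any time. Concomitant surgery is tested against effectiveness. Such items can follow from response or from time on drug.

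At stake is whether objective 3 yields anything that can be interpreted. A reader of the report would see p-values below 0.05 called significant, without a comparative effect size, its precision, or any indication of which linked factor carries the association. The SAP supports the regulatory report and the re-examination application (SAP 3.1).

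**Working it through.** **The plan's own figure.** The documents give no error rate or test count for these tables. Their quantitative target is the precision of the remission rate: 1500 × 0.30 × 0.70 = 315 patients with a Mayo score, and 1.96 × √(0.30 × 0.70 / 315) = 5.06%, giving 24.9% to 35.1%. This reproduces Table 1, but it says nothing about factor comparisons.

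**Number of factors (list under Table 2.9, repeated under 3.4, borrowed by 3.4.1).**
- Demographics and duration of illness: 7
- Complications: 8
- Medical history: 8
- Allergy, smoking (two items), self-administration: 4
- Prior medication: 10
- Prior treatment: 5
- Concomitant medication: 7
- Concomitant treatment: 5
- Disease site, partial Mayo score, CRP: 3

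Sum: 57 per table, 171 over three tables. By contrast, Bonferroni is used in 3.1.1 and 3.1.4, which by the periods in SAP 12.3 and 12.4 have at most 4 and 7 comparisons with baseline.

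**Chance findings if all factors were null.**
- Expected number per table: 57 × 0.05 = 2.85. Over three tables: 171 × 0.05 = 8.55.
- At least one per table, independent tests of full size: 1 − 0.95^57 = 94.6%.
- With 20, 30 or 40 effective independent tests: 1 − 0.95^20 = 64%, 1 − 0.95^30 = 79%, 1 − 0.95^40 = 87%. Overlap lowers this probability but not the expected count.
- Fisher's test is conservative for rare factors, which lowers both. Assuming N = 1500 and a reaction rate of 10% or 20% (no rate is given in the documents), the actual size from the hypergeometric distribution is 0% for a factor held by 1 patient, 0.7% to 0.8% for 5 patients, 1.3% to 3.2% for 10, and 4.0% to 4.8% for 150 to 750.
- Table 2.9 is read here as testing adverse reactions only. If serious reactions were tested too, it would have 114 tests and 114 × 0.05 = 5.7 expected.

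**Cost of a strict correction.** Take the plan's own contrast, 10% of 252 against 30% of 63. The pooled rate is 44.1/315 = 0.14. The standard error is √(0.14 × 0.86 × (1/252 + 1/63)) = 0.0489 under the null and √(0.09/252 + 0.21/63) = 0.0607 under the alternative. Power is Φ((0.20 − z × 0.0489)/0.0607): 95.7% at 0.05, and 73.1% at 0.05/57 = 0.00088.

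**Room for a model.** With the levels in SAP section 11, the nine baseline factors named in the fix need 2 (age) + 1 (sex) + 2 (duration) + 1 (biologic history) + 2 (partial Mayo) + 2 (CRP) + 1 (steroids) + 1 (thiopurines) + 2 (site by type) = 14 parameters, or 16 with an unknown level for partial Mayo and CRP. At the assumed 10% to 20% reaction rate, 150 to 300 events give 9.4 to 18.8 per parameter in Table 2.9. The number of remissions available for 3.4.1 is not given.

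**The case against.** The survey is exploratory. SAP 4.1 speaks of exploring these items, and Protocol 13(2) allows for a further survey or study when questions arise. A safety screen should not lose real signals to strict error control, and the fall in power from 95.7% to 73.1% shows the price of Bonferroni. This stands: family-wise control is not needed, and a q-value column is a matter of preference. It does not answer the missing comparative estimates or the missing adjustment for linked factors. The tables carry no exploratory label either, and SAP 13.3 calls the outcomes of 3.4 and 3.4.1 primary endpoints.

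A reader might infer three stronger points that the documents do not support:
- *That no effect information is given.* Percentages per level are reported, and crude contrasts follow from them by arithmetic. What is missing is the contrast itself, its interval and any adjusted version.
- *That false factors are certain to be reported, about three per table.* The figures 2.85, 95% and 8.55 are upper-end values. They assume that every factor is null, which the plan's own 10% against 30% contradicts for anti-TNF history. The 95% also assumes independence among factors that are partly nested (age, elderly and pediatrics; biological product and infliximab).
- *That selection into 2.9.xx hides results.* It only adds descriptive tables. Self-administration, hepatic and renal disorder, children, the elderly and biologic history have their own tables (2.5, 2.13.1 to 2.16.1, 2.18) whatever the p-value.

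**Conclusion.** The point holds as a worthwhile improvement to the method for a stated objective. It is not a defect that invalidates the survey. The factor count, the unadjusted 5% level and the absence of comparative estimates, intervals and adjusted analyses can all be read directly from the SAP.

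Chance findings are likely rather than certain. Under a global null the ceiling is 2.85 per table, with a probability of at least one of about 64% to 95% depending on how far the tests overlap, and less where factors are rare. Confounding is the weightier half of the point, but it rests on the design (one-at-a-time comparisons in non-randomised data) and not on a number. No figure in the documents shows how strongly the factors move together.

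**What to change.** In Tables 2.9, 3.4 and 3.4.1:

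1. Add unadjusted odds ratios with 95% confidence intervals beside the percentages.
2. Add one pre-specified logistic model per table with baseline factors already collected: age, sex, duration of illness, history of biological products, baseline partial Mayo score, baseline CRP, steroid use at start, thiopurine use at start, and disease site.
3. State that drug use at start is a new derived variable, different from the SAP's concomitant use. Table 3.6 already identifies steroid users at start, and the case report form collects administration periods for ulcerative colitis drugs.
4. State how missing baseline values are handled. SAP 9.1 generally imputes nothing, and SAP 9.5 leaves unknown values out of tests. Either keep these patients through the existing unknown/not provided level for partial Mayo and CRP, or report how many are dropped.
5. Say in advance how the model is reduced if a table has too few events.
6. Label the single-factor p-values, and the 2.9.xx tables they select, as exploratory. A q-value column is optional.

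No new data are needed. The cost is one model and a few columns per table, the derivation of two variables, possible loss of patients with missing baseline values, and fewer factors described as significant.

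### The serious-reaction breakdown in Table 2.9.xx is triggered only by a test of all adverse reactions, which can have low power for a factor that raises mainly serious reactions

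*SAP*

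**What the plan says.** SAP 4.1 lists among the objectives "Factors which may affect the safety and effectiveness". Table 2.9 (SAP 13.2) serves the safety half of it. For each of 57 listed background factors it gives "the percentage to the number of patients with serious adverse reactions and all patients", the same for all adverse reactions, and "the tests for adverse reactions (Fisher's exact test for nominal-scale factors and Man-Whitney's u test for ordinal-scale factors"). No test of serious adverse reactions is named, although the table title mentions both outcomes. SAP 9.6 sets the threshold: "In principle, the significant level is 5%, two-tailed". Table 2.9 states no multiplicity adjustment.

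Table 2.9.xx is the follow-on table, with non-serious and serious reactions by system organ class (SOC) and preferred term (PT). Its stated purpose is "to show the onset status of non-serious/serious adverse reactions per statistically-significant background factor based on the test results in 2.9".

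Four factors get a seriousness split whatever the p-value: Table 2.13.1 ("to show the onset status of non-serious/serious adverse reactions with/without hepatic function disorder"), Table 2.14.1 ("to show the onset status of non-serious/serious adverse reactions with/without renal impairment"), Table 2.15.1 (pediatric) and Table 2.16.1 (elderly). Self-administration and biologic history have fixed SOC/PT tables (2.5 and 2.18), but without a seriousness split.

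**The concern.** The outcome that is tested is not the outcome that 2.9.xx is meant to break down. Serious reactions are a subset of all reactions. If a factor acts mainly on the serious ones, its effect is diluted by the non-serious reactions, and the test may not reach 5% even when the serious risk differs substantially.

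The factor then has no SOC/PT table by seriousness. A reader of 2.9 would see a higher serious percentage without a test on it, and would not see from these tables whether the excess was infection, malignancy or something else. That matters here because infection, tuberculosis and malignant tumour are priority survey items and the listed factors include concomitant corticosteroids, thiopurines and calcineurin inhibitors. Nothing in the SAP says that absence from 2.9.xx is not evidence of no risk.

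**Working it through.** **The plan's own safety figure.** SAP 4.3 and protocol section 2 support 1500 patients by the interval for a 2% tuberculosis incidence. The Clopper-Pearson interval for 30/1500 is 1.35% to 2.84%, as stated. It describes one incidence in the whole group. The documents give no power for the comparisons in Table 2.9.

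**Inputs from the documents.** N = 1500 (protocol section 2, "The number of patients to be included: 1500"), which is an upper bound for the safety analysis group; two-sided 5%; Fisher's exact test for a yes/no factor.

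**Assumed inputs, not in the documents.** Without the factor, a proportion s of patients has a serious reaction and q has non-serious reactions only. The factor multiplies s by 2 and q by m. Factor prevalence is 5 to 40%. The planned trigger compares 2s + mq with s + q. A serious-reaction test compares 2s with s.

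**One cell by hand** (s = 4%, q = 20%, m = 1, prevalence 20%, so 300 exposed and 1200 not). Power ≈ Φ[(d − 1.96·SE0)/SE1], with SE0 pooled and SE1 unpooled. In both comparisons d = 0.04.

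- Trigger, 28% v 24%: the pooled rate is (84 + 288)/1500 = 0.248. SE0 = √(0.248 × 0.752 × (1/300 + 1/1200)) = 0.0279. SE1 = √(0.28 × 0.72/300 + 0.24 × 0.76/1200) = 0.0287. Power ≈ Φ(−0.51) = 0.31, so about 70% are missed.
- Serious reactions, 8% v 4%: the pooled rate is (24 + 48)/1500 = 0.048. SE0 = 0.0138. SE1 = √(0.08 × 0.92/300 + 0.04 × 0.96/1200) = 0.0167. Power ≈ Φ(0.78) = 0.78, so about 22% are missed.

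The difference is the same 4 points. Only the background variance differs.

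**All cells.** Exact power sums the two binomial probabilities over every pair of counts for which two-sided Fisher rejects at 5%. Percentage of surveys in which the factor is missed:

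| s, q, m | Test | 5% prev. | 10% | 20% | 40% |
|---|---|---|---|---|---|
| 4%, 20%, 1 | all reactions (trigger) | 88 | 82 | 71 | 60 |
| | serious reactions | 65 | 46 | 24 | 11 |
| 6%, 20%, 1 | all reactions (trigger) | 80 | 67 | 47 | 30 |
| | serious reactions | 52 | 29 | 9 | 2 |
| 10%, 10%, 1 | all reactions (trigger) | 50 | 23 | 5 | 1 |
| | serious reactions | 31 | 9 | 1 | 0 |
| 5%, 15%, 1 | all reactions (trigger) | 83 | 71 | 54 | 39 |
| | serious reactions | 61 | 37 | 15 | 5 |
| 5%, 15%, 1.25 | all reactions (trigger) | 59 | 34 | 12 | 3 |
| | serious reactions | 61 | 37 | 15 | 5 |
| 4%, 20%, 1.25 | all reactions (trigger) | 61 | 36 | 13 | 4 |
| | serious reactions | 65 | 46 | 24 | 11 |

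With m = 1 the trigger is the weaker test in every cell, and the gap is small only where both tests rarely miss. If the factor also raises non-serious-only reactions by 25% (m = 1.25), the trigger does as well or better. Neither test dominates, which argues for letting either one trigger the table. Ordinal factors, tested by Mann-Whitney, were not computed.

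**The case against.** The strongest reply is that little is withheld. Table 2.9 prints the serious count and percentage for every factor whatever the p-value, so a doubling from 4% to 8% would be visible there. Listing 1.4.1 gives the seriousness of each event and the patient's complications by PT, so serious events in patients with diabetes, for example, can be traced. Tables 2.4.1 to 2.4.4 count serious cases for every priority item and identified risk. All of this stands. It limits the loss to the SOC/PT detail by factor and to a test on serious reactions. It does not remove the loss: 2.4.1 to 2.4.4 are not split by factor, and 1.4.1 does not list concomitant drugs (1.4.3 does, but only for patients with cytomegalovirus infection).

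The second reply is that the figures depend on assumed rates and on an effect confined to serious reactions. That also stands, as the lower rows of the table show.

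The third is that the title of Table 2.9 names both outcomes, so tests on both may have been intended. That is possible, but the analysis items name one, and the SAP should say which.

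A reader might be tempted to go further and conclude that a factor doubling serious reactions would usually be dropped, or that a non-significant result rules out any look at its serious reactions. The documents do not support either. They give no expected reaction rates, and a prevalence only for prior anti-TNF use; with 10% serious reactions and a factor present in 10% or more of patients, the trigger works in most surveys. The serious percentage is never suppressed.

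**Conclusion.** The point holds in a limited form. As worded, a test of all adverse reactions alone decides which of 53 factors (57 less the four with fixed tables) receive a breakdown of serious reactions by SOC and PT. For a factor acting mainly on serious reactions, that trigger misses about 30 to 88% of surveys where a serious-reaction test misses about 2 to 65% (prevalence 40% down to 5%). This assumes 1500 patients in the safety group, 4 to 6% serious and 20% non-serious-only reactions, a doubled serious risk and no effect on non-serious-only reactions. A smaller safety group would lower the power of both tests. The gap narrows at serious rates near 10% and closes or reverses if non-serious-only reactions rise by 25%. This is a cheap improvement to an exploratory safety table that serves a stated objective; it is not a flaw that hides serious reactions.

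**What to change.** 1. In Table 2.9, add the same Fisher or Mann-Whitney test for serious adverse reactions. If it was already intended, say so.
2. In Table 2.9.xx, change the trigger to p<0.05 for adverse reactions or for serious adverse reactions.
3. Optionally, show 2.9.xx whatever the p-value for the concomitant immunosuppressants already on the list (corticosteroids, azathioprine & 6-mercaptopurine, tacrolimus & ciclosporin). Extending this to rare medical histories would add little: at an assumed 8% serious rate, 15 to 30 exposed patients give 15 × 0.08 = 1.2 to 30 × 0.08 = 2.4 serious cases, so the tables would be nearly empty.
4. State that a non-significant factor has not been shown to be without risk.

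The cost is SAP wording, one more test column and some extra pages in an existing layout; no new data are needed. Under no effect, the added tests bring at most about 57 × 0.05 = 2.85, or 3, further chance flags, so they should be labelled exploratory. Even the serious-reaction test misses many effects at 5% prevalence, which is why the sentence in item 4 is needed whichever trigger is used.
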